4.4.4 Sensitivity Analyses

A descriptive summary of additional post-surgery bleeds requiring BPA/FVIII use beyond the first treated bleed will be presented without any formal statistical testing in order to observe how additional treated bleeds after discharge from the surgery were distributed in the study. Specifically, the percentage of patients with 0 bleeds, 1 bleed, 2 bleeds, 3 bleeds and >3 bleeds will be summarized separately for each of the inhibitor and non-inhibitor cohort and will be displayed overall and by surgery type.

4.4.5 Subgroup Analyses

Not applicable.

4.5 PHARMACOKINETIC AND PHARMACODYNAMIC ANALYSES

Mean and median emicizumab concentrations at the beginning of the surgery will be summarized separately for each of the inhibitor and non-inhibitor cohorts and will be displayed overall and by surgery type.

4.6 SAFETY ANALYSES

Safety will be assessed through descriptive summaries of safety endpoints, adverse events, and vital signs.

4.6.1 Exposure of Study Medication

Information on emicizumab administration after discharge from surgery will be collected on the Bleed and Medication Diary and summarized by presenting the percentage of patients who took their emicizumab as prescribed at each visit as well as the mean/median dose taken. These analyses will be performed separately for the inhibitor and non-inhibitor cohorts and will be displayed overall and by surgery type.

4.6.2 Adverse Events

All adverse events occurring after informed consent is obtained will be coded. Treatment emergent events will be summarized by severity, and tabulated by body system and preferred term for individual events within each system organ class. In addition, serious adverse events, adverse events of special interest (AESIs), and adverse events leading to study discontinuation will be summarized. All serious adverse events and deaths will be listed.

Non-treatment-emergent events will be identified through two entries on the “Adverse Events” CRF page: response to “Action taken with emicizumab due to SAE/AE” is “Not applicable” AND response to “Date of most recent dose of Emicizumab prior to AE onset” is missing. These events will not be included in the treatment emergent safety analysis, but will be included in Adverse Event listing with an appropriate flag.

The safety endpoint, “Percentage of patients with surgical complications requiring hospitalization or return to surgery”, is a composite endpoint. Surgical complications are entered as adverse events on the “Adverse Events” CRF page with “Other suspected causes” marked as “Study Surgery or Procedure”. This endpoint is met when response to “It required or prolonged inpatient hospitalization” is checked OR response to response to “Was procedure/surgery performed?” is “Yes”.

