#### **4.4.2 Prohibited Therapy**

Use of the following therapies is prohibited during the study and for at least 4 weeks prior to study start unless otherwise noted:

- Drugs that would affect hemostasis (e.g., aspirin, non-steroidal anti-inflammatory drugs that are not selective or preferential cyclooxygenase-2 [COX-2] inhibitors, or anticoagulants [other than to flush, dwell, or de-clot a CVAD]) but excluding drugs intended to control bleeding episodes or used in the context of minor surgery (e.g., tooth extraction) or injuries (e.g., concussion) to prevent deterioration
- Systemic immunomodulators (e.g., rituximab, interferon) other than antiretroviral therapy from enrollment to last observation
- FVIII or BPA for prophylaxis or for the treatment of a breakthrough bleed within 24 hours prior to surgery
- Other investigational drugs from enrollment to last observation

If prohibited therapy is administered for any reason, it should be recorded on the eCRF. If prohibited treatment is prescribed or considered medically necessary, the medical monitor should be consulted to discuss any changes in the benefit/risk and determine whether the patient should continue on the study.

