##### **4.5.1 Informed Consent Forms and Screening Log**

Written informed consent for participation in the study must be obtained before performing any study-related procedures (including screening evaluations). Children and adolescents (< 18 years of age) will complete an Assent Form when capable and their parents or legally authorized representatives will also complete an Informed Consent Form. Informed Consent Forms for enrolled patients and for patients who are not subsequently enrolled will be maintained at the study site.

All screening evaluations must be completed and reviewed to confirm that patients meet all eligibility criteria before enrollment. The investigator will maintain a screening log to record details of all patients screened and to confirm eligibility or record reasons for screening failure, as applicable.

If the screening period extends beyond the 60-day window allowed by the protocol for any reason, the patient should be re-consented prior to the expiration of the original 60-day screening window. The complete screening evaluations should also be repeated and documented following the re-consent. Only one extension of the screening period with proper re-consent will be allowed for a patient.

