### **5.2.1 Adverse Events**

According to the ICH guideline for Good Clinical Practice, an adverse event is any untoward medical occurrence in a clinical investigation subject administered a pharmaceutical product, regardless of causal attribution. An adverse event can therefore be any of the following:

- Any unfavorable and unintended sign (including an abnormal laboratory finding), symptom, or disease temporally associated with the use of a medicinal product, whether or not considered related to the medicinal product
- Any new disease or exacerbation of an existing disease (a worsening in the character, frequency, or severity of a known condition), except as described in Section 5.3.5.10

- Recurrence of an intermittent medical condition (e.g., headache) not present at baseline
- Any deterioration in a laboratory value or other clinical test (e.g., ECG, X-ray) that is associated with symptoms or leads to a change in study treatment or concomitant treatment or discontinuation from study drug
- Adverse events that are related to a protocol-mandated intervention, including those that occur prior to Study Day 1 (e.g., screening invasive procedures such as biopsies, *or additional surgical procedures unrelated to the primary surgery*)

All bleeds will be recorded on the bleed/medication diary. Bleeds meeting the criteria of serious adverse events (as per Section 5.2.2) should be reported on the appropriate adverse event eCRF page regardless of whether the bleeds are consistent with patients' pre-study disease state. New, non-serious bleeds consistent with patients' pre-study disease state will not be considered adverse events.

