2. STUDY DESIGN

This Phase IV, multicenter study will evaluate whether PwHA receiving emicizumab prophylaxis can safely undergo minor surgical procedures without additional prophylaxis with BPAs for patients with inhibitors or FVIII for patients without inhibitors. Current guidelines recommend a pre-operative dose of BPA/FVIII as surgical prophylaxis, but in patients on emicizumab prophylaxis in this study, additional pre-operative prophylaxis with BPA/FVIII will not be used. The use of BPA/FVIII for excessive surgical bleeding will be measured intraoperatively and postoperatively. In addition, surgical complications from bleeding and blood product transfusions will be evaluated. This study will assess emicizumab prophylaxis alone to control surgery-related bleeding in PwHA undergoing minor surgical procedures.

[figure not shown]
Patients can be screened and enrolled up to 60 days prior to surgery. They must have received a minimum of four loading doses of emicizumab prior to their surgical procedure, been adherent with emicizumab prophylaxis, and must not have received BPA/FVIII for at least 24 hours prior to surgery. In addition, they must plan to continue emicizumab prophylaxis for at least 1 month after the surgical procedure. Follow-up will be conducted by phone on Study Days 2 and 3 (approximately 24 and 48 hours post operation) to record any BPA/FVIII use and surgical bleeding within the first 48 hours, as well as treatment of any other bleeding unrelated to surgery. BPA/FVIII should only be used for treatment of bleeding. Follow-up will be conducted in person on Study Day 8 (± 2 days) to examine the patient for any postsurgical complications and to collect information on treatment of bleeding. Lastly, follow-up will be conducted by phone on Study Day 28 (± 2 days) to record any surgical complications, bleeds, and/or use of BPA/FVIII (see Appendix 2).

Blood samples will also be collected in this study for observational purposes and will not be used to determine eligibility or treatment decisions. Samples will be used to evaluate emicizumab concentration (PK) prior to surgery.

Safety follow-up will be conducted after signing the informed consent form and patients will be monitored for adverse events as noted above to evaluate the safety of emicizumab alone or in combination with BPA/FVIII.

Figure 1 shows the study schema.

Figure 1 Study Schema

FVIII= factor VIII; US= United States.

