- ⁱ Includes evaluation of the head, eyes, ears, nose, and throat, and the cardiovascular, respiratory, gastrointestinal, and dermatologic systems. Focused examination of the musculoskeletal, genitourinary, and neurological systems should be performed as related to the surgical procedure. Record abnormalities observed at baseline on the General Medical History and Baseline Conditions eCRF. At subsequent visits, record new or worsened clinically significant abnormalities on the Adverse Event eCRF.
- ^j Perform a limited, symptom-directed examination at specified timepoints or as clinically indicated. Record new or worsened clinically significant abnormalities on the Adverse Event eCRF.
- ^k Site must document that patient was clinically stable and not actively bleeding prior to discharge.
- ^l Hematology includes complete blood count with differential (i.e., neutrophils, hemoglobin, platelet count).
- ^m Chemistry panel includes sodium, potassium, chloride, glucose, blood urea nitrogen, creatinine, calcium, phosphorus, magnesium, total and direct bilirubin, total protein, albumin, alanine aminotransferase, aspartate aminotransferase, lactate dehydrogenase, alkaline phosphatase, and creatine phosphokinase).
- ⁿ PK sample must be obtained at the study site 24 hours before surgery.
- ^o Medication (e.g., prescription drugs, over-the-counter drugs, vaccines, herbal or homeopathic remedies, nutritional supplements) used by a patient in addition to protocol-mandated treatment from 28 days prior to surgery until Study Day 28.

- Ⓟ After informed consent has been obtained, all adverse events will be reported until Study Day 28. After this period, adverse events should be reported per routine reporting requirements. In addition, the Sponsor should be notified if the investigator becomes aware of any serious adverse event that is believed to be related to prior study drug treatment. The investigator should follow each adverse event until the event has resolved to baseline grade or better, the event is assessed as stable by the investigator, the patient is lost to follow-up, or the patient withdraws consent. Every effort should be made to follow all serious adverse events considered to be related to study drug or trial-related procedures until a final outcome can be reported.

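### SAP 4.6.2 pools adverse events from before and after surgery in one summary, and SAP 4.6 assigns no analysis population to any safety summary

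*SAP*

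**What the plan says.** - **Window.** SAP 2: "Patients can be screened and enrolled up to 60 days prior to surgery". SAP 3 treats signing consent as enrollment. SAP Appendix 2: "After informed consent has been obtained, all adverse events will be reported until Study Day 28". Protocol 5.4.2 sets the same period for SAEs and AESIs.
- **Filter.** SAP 4.6.2: "Non-treatment-emergent events will be identified through two entries on the" adverse-event form. An event is non-treatment-emergent only if the action taken with emicizumab is not applicable and the date of the last emicizumab dose is missing. Such events leave the tables but "will be included in Adverse Event listing with an appropriate flag". The SAP does not say whether the SAE and AESI summaries use the same filter.
- **Surgery-linked safety endpoints.** SAP 2.2.5 has two: surgical complications leading to hospitalization or return to surgery, and transfusion during surgery. SAP 4.6.2 identifies the first through the suspected-cause entry on the form.
- **Populations.** SAP 4.1 defines All Enrolled and Efficacy only. SAP 4.2, 4.3 and 4.4 each name one; SAP 4.6 names none. Protocol section 6, and the synopsis copied into SAP Appendix 1, also define a Safety Analysis Population: enrolled patients who receive emicizumab, with no surgery requirement. Neither document assigns it to a summary.
- **Aim.** SAP 2 says the study will "evaluate whether PwHA receiving emicizumab prophylaxis can safely undergo minor surgical procedures" without added bypassing agent (BPA) or FVIII prophylaxis.

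**The concern.** The study's question starts at the operation, because that is when withholding BPA or FVIII prophylaxis can have an effect. A patient who consents weeks earlier contributes ordinary emicizumab follow-up until then. If both stretches feed one row per AE term, the tables do not show AE or AESI incidence from surgery onward.

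The AESI row matters most. Protocol 5.1.1.1 links thrombotic microangiopathy and thrombotic events to aPCC, a bypassing agent, given with emicizumab. The protocol permits BPA to treat bleeds, and the pre-surgical restriction in Protocol 4.4.2 is limited in time: "FVIII or BPA for prophylaxis or for the treatment of a breakthrough bleed within 24 hours prior to surgery". In the inhibitor cohort, therefore, an event after BPA for a bleed weeks before surgery and an event after BPA for surgical bleeding would be counted together, although only the second bears on the study question.

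The population gap is a separate matter. A percentage of patients transfused during surgery makes sense only among patients who had surgery, and the one safety population defined does not require it.

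**Working it through.** **1. The plan's own figure.** The plan gives no figure on AE timing. Its only computed figures are the exact limits in Protocol Table 5 (SAP Table 1). With Clopper-Pearson, lower = Beta(0.025; x, n−x+1) and upper = Beta(0.975; x+1, n−x). All 12 limits reproduce to three decimals; for example, 3/30 gives 0.021 to 0.265. The same method is used in step 4.

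**2. Share of observation time before surgery.** The schedule runs from Day −60 to Day −1, then Day 1 (surgery) to Day 28. For a patient already on emicizumab at consent, with g days from consent to surgery and p days from surgery to the last call, the share is g/(g+p). The limit of 60 is in the documents; gaps of 14 and 30 days are assumptions, since actual gaps are not given. The Day 28 call has a window of ±2 days.

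| g | p = 28 | p = 26 | p = 30 |
|---|---|---|---|
| 14 | 14/42 = 33% | 14/40 = 35% | 14/44 = 32% |
| 30 | 30/58 = 52% | 30/56 = 54% | 30/60 = 50% |
| 60 | 60/88 = 68% | 60/86 = 70% | 60/90 = 67% |

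For such a patient a last-dose date exists, so the filter removes little. Protocol 4.2 says all enrolled patients are receiving emicizumab, but Protocol 4.1.1 lets loading doses still be planned at entry. For a patient who starts after consent, the treatment-emergent table begins at first dose, which is still before surgery.

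**3. What is already tied to surgery.**

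| Outcome | Tied to surgery by |
|---|---|
| Bleeding with BPA/FVIII use | Start of surgery to discharge, and after discharge (SAP 2.2.1) |
| Transfusion | Limited to during surgery (SAP 2.2.5) |
| Complications with hospitalization or a procedure | Attribution to surgery (SAP 4.6.2) |
| Other AEs, and AESIs as such | Nothing |

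An AESI attributed to BPA and not to the operation, or an AE without hospitalization or a procedure, would not meet the complication endpoint.

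**4. Denominator.** Assume 30 treated patients, of whom 0% to 30% never have surgery; the documents give no rate.

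| Operated | 3 events / operated | Exact 95% CI | Upper limit with 0 events |
|---|---|---|---|
| 30 | 10.0% | 2.1–26.5% | 11.6% |
| 27 | 11.1% | 2.4–29.2% | 12.8% |
| 24 | 12.5% | 2.7–32.4% | 14.2% |
| 21 | 14.3% | 3.0–36.3% | 16.1% |

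Using all 30 treated patients would report 10.0% in every row. The largest difference is 14.3 − 10.0 = 4.3 percentage points, against an interval width of 26.5 − 2.1 = 24.4 points at 3/30.

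**The case against.** The endpoint is the incidence and severity of all AEs, and monitoring from consent serves the stated aim of describing emicizumab alone or with BPA/FVIII. SAP 4.6.2 delivers that and agrees with Protocol 6.5. The direct harm of withholding prophylaxis is bleeding, which already has surgery-based windows, and new non-serious bleeds consistent with pre-study disease are not AEs (Protocol 5.2.1). A split AE table would not show them.

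Counts will also be very small. Protocol 5.1.1.1 reports microangiopathy in 3 of 391 patients and thrombotic events in 2 of 391. If these were different patients, 5/391 = 1.3%, or 30 × 5/391 = 0.4 expected in 30 patients, assuming the pooled rate carries over. The study is descriptive and was terminated early, and SAP 4 falls back to listings when data are sparse. Because Study Day is anchored to surgery, a listing showing it would place each event.

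Much of this stands. The emicizumab-based table is legitimate, and the split would matter for few events. It does not remove the gap: the SAP does not say that any listing shows onset relative to surgery, and with very few AESIs the timing of each one carries most of the information. The argument also leaves the missing population untouched.

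**Conclusion.** Minor. The general AE, SAE and AESI summaries pool pre-surgery and later events, with up to 68% of observation time before surgery (67–70% over the Day 28 window) for a patient already on emicizumab who consents at the 60-day limit. The loss is confined to AEs without a surgery-linked endpoint and to AESIs. Separately, no safety summary has an assigned population. The effect on the two surgical percentages is small against their intervals and depends on an unknown number of patients who never have surgery. No hypothesis test or sample size is affected.

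A reader might infer more than the documents support:

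- **That most reported AEs will predate surgery.** Time shares equal event shares only at a constant AE rate, which is implausible when one period contains an operation.
- **That re-consent pushes the share above these figures.** Protocol 4.5.1 says "Only one extension of the screening period with proper re-consent will be allowed for a patient", but screening is then repeated, Appendix 1 makes the consent date the enrollment date, and surgery must fall within 60 days of enrollment. Nothing says AEs are counted from a first consent after re-consent.
- **That the protocol expects AEs before surgery.** Protocol 5.2.1 includes "Adverse events that are related to a protocol-mandated intervention, including those that occur prior to Study Day 1" in its AE definition. That defines what would count; it does not predict that any will occur.
- **That the BPA example applies to both cohorts.** BPA use is specific to the inhibitor cohort.
- **That surgical safety goes unassessed.** Bleeding, transfusion and surgery-attributed complications are all covered.

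**What to change.** 1. Keep the emicizumab-based treatment-emergent table. In SAP 4.6.2 add, for each cohort, AEs, SAEs and AESIs in two columns: onset before surgery, and onset from the start of surgery to Study Day 28. Use operated patients as the denominator of the second column. State in advance that Day 1 events without an onset time go in the second column.
2. If summaries become listings under SAP 4, require Study Day of onset for every event. This alone would close most of the timing gap.
3. Restore the Safety Analysis Population in SAP 4.1 and name it in SAP 4.6 for the overall AE tables.
4. Use the Efficacy Analysis Population (operated patients) for surgical complications and for transfusion during surgery.

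Cost: SAP wording and a little programming, using only AE onset and surgery dates. The added columns will be sparse and should be read as description only.

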## **4.3 STUDY TREATMENT AND OTHER TREATMENTS RELEVANT TO THE STUDY DESIGN**

### **4.3.1 Study Treatment**

#### **4.3.1.1 Emicizumab**

If a patient is prescribed emicizumab for prophylaxis, emicizumab is administered 3 mg/kg/week subcutaneously for the first 4 weeks when initiating treatment (loading doses), followed by 1.5 mg/kg/week subcutaneously or by any other approved maintenance regimen. Patients must have received all loading doses and been adherent to emicizumab prophylaxis prior to surgery and plan to continue emicizumab for a minimum of 1 month after surgery. For the purposes of this protocol, study treatment is not intended to imply that the Sponsor is providing the study drug; rather, emicizumab is required for all patients during the study per the inclusion and exclusion criteria (see Sections 4.1.1 and 4.1.2).

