#### **4.5.5 Bleed and Medications Diary**

Patients (or patient's legally authorized representative) will complete the bleed/medication diary; one diary card per week for 4 weeks after being discharged from surgery. Information obtained will include start date and time, reason, type, location of each bleed, as well as start date and time, reason, type, and dose of each injection, if any, including emicizumab. Diary entries for events should be completed on the cards as soon as events occur.

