- j Perform a limited, symptom-directed examination at specified timepoints or as clinically indicated. Record new or worsened clinically significant abnormalities on the Adverse Event eCRF.
- k Site must document that patient was clinically stable and not actively bleeding prior to discharge.
- l Hematology includes complete blood count with differential (i.e., neutrophils, hemoglobin, platelet count).
- m Chemistry panel includes sodium, potassium, chloride, glucose, blood urea nitrogen, creatinine, calcium, phosphorus, magnesium, total and direct bilirubin, total protein, albumin, alanine aminotransferase, aspartate aminotransferase, lactate dehydrogenase, alkaline phosphatase, and creatine phosphokinase).
- n PK sample must be obtained at the study site 24 hours before surgery.
- o Medication (e.g., prescription drugs, over-the-counter drugs, vaccines, herbal or homeopathic remedies, nutritional supplements) used by a patient in addition to protocol-mandated treatment from 28 days prior to surgery until Study Day 28.

Appendix 1  
Schedule of Activities (cont'd)

- Ⓐ After informed consent has been obtained, all adverse events will be reported until Study Day 28. After this period, adverse events should be reported per routine reporting requirements. In addition, the Sponsor should be notified if the investigator becomes aware of any serious adverse event that is believed to be related to prior study drug treatment. The investigator should follow each adverse event until the event has resolved to baseline grade or better, the event is assessed as stable by the investigator, the patient is lost to follow-up, or the patient withdraws consent. Every effort should be made to follow all serious adverse events considered to be related to study drug or trial-related procedures until a final outcome can be reported.
- Ⓐ Patients (or patient's legally authorized representative) will complete the bleed/medication diary and will include start date and time, reason, type, location of each bleed, as well as start date and time, reason, type, and dose of bypassing agent, if any, excluding emicizumab.

## Appendix 2

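### When action taken with emicizumab is Not applicable, SAP 4.6.2 lets a missing last-dose date make an adverse event non-treatment-emergent, without checking onset against the first dose (minor)

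*SAP*

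**What the plan says.** SAP 4.6.2 states that "Non-treatment-emergent events will be identified through two entries on the" adverse event CRF page. The first entry is "Action taken with emicizumab due to SAE/AE", which must be Not applicable. The second is "Date of most recent dose of Emicizumab prior to AE onset", which must be missing. The two are joined by AND. On the consequence the SAP says: "These events will not be included in the treatment emergent safety analysis, but will be included in Adverse Event listing with an appropriate flag". The same section lists all serious adverse events and deaths, and codes every event from informed consent onward.

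On exposure, protocol 4.3.1.1 says: "Patients must have received all loading doses and been adherent to emicizumab prophylaxis prior to surgery". Protocol 3.1 and 4.3.2 also require the loading doses before surgery. Entry is looser: under protocol 4.1.1, a plan to receive the loading doses is enough, so a patient may consent before the first dose.

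SAP 4.7 gives a rule for incomplete dates of adverse events, concomitant medication and laboratory data. It does not name the emicizumab dose date.

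**The concern.** Treatment-emergent status is a question of timing: did the event start before or after the first dose? SAP 4.6.2 answers it from two data-entry states. A blank last-dose date can mean that no dose had been given, or that a dose was given and its date was not recorded. The SAP does not separate the two.

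Before the first dose, the blank is the expected entry. After surgery it cannot be, because every operated patient should have completed loading. An on-drug event with both entries in that state would drop out of the treatment-emergent tables. Incidence and severity of adverse events is a safety endpoint (SAP 2.2.5), reported separately for two small cohorts, so a single patient moves the percentage visibly.

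**Working it through.** **1. The rule as a truth table (SAP 4.6.2).**

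| Action taken | Last-dose date | Class |
|---|---|---|
| Not applicable | missing | non-treatment-emergent |
| Not applicable | present | treatment-emergent |
| any other | missing | treatment-emergent |
| any other | present | treatment-emergent |

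One of the four combinations removes an event. A missing date alone never does.

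**2. The rule against the exposure timeline.**

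- *Consent to first dose.* Events are collected, no dose has been given, and a blank date is correct. The rule works here if action taken is entered as Not applicable. If another action is entered, a true pre-dose event is counted as treatment-emergent.
- *First dose to surgery.* A dose has been given. A blank date is a data gap, and with Not applicable the rule misclassifies the event.
- *Study Day 1 onward, operated patients.* All loading doses precede surgery (protocol 3.1, 4.3.1.1, 4.3.2). Barring a protocol deviation, every event follows a dose, so whenever the rule fires here it is wrong.

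**3. How often.** The share of on-drug events removed is

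P(action Not applicable) × P(date missing given Not applicable).

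The documents give neither probability. Assuming 5% to 50% for the first and 5% to 20% for the second:

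- low end: 0.05 × 0.05 = 0.0025, or 0.25% of on-drug events;
- high end: 0.50 × 0.20 = 0.10, or 10%.

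This range shows only what the assumptions imply. It is not an estimate for this trial.

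**4. What one lost patient does.** The plan states no figure for this rule. Its only related figures are the Clopper-Pearson limits in the precision table (protocol Table 5, SAP Table 1). With x events in n patients, the lower limit is the 0.025 quantile of Beta(x, n−x+1) and the upper limit is the 0.975 quantile of Beta(x+1, n−x). All six rows reproduce to three decimals, including 2/20 (0.012 to 0.317) and 3/30 (0.021 to 0.265).

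The same formula, with assumed counts and one patient wrongly removed, gives:

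- n = 20: 2/20 = 10% (1.2% to 31.7%) becomes 1/20 = 5% (0.1% to 24.9%), a fall of 1/20 = 5 points;
- n = 30: 3/30 = 10% (2.1% to 26.5%) becomes 2/30 = 6.7% (0.8% to 22.1%), a fall of 1/30 = 3.3 points.

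The SAP says that the study is ending early with limited samples but gives no final number. The fall is 1/n in general. It reaches the any-event percentage only if the patient has no other treatment-emergent event.

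**The case against.** The best defence is that the rule is narrow and its effects visible. It needs a positive response of Not applicable as well as a blank date, and nothing in the documents shows that sites would choose that response for a patient on drug. A true pre-dose event has no prior dose date and no applicable drug action, so the pair is a reasonable marker for what it is meant to catch. Removed events remain in a flagged listing, and serious events and deaths are listed in any case. The surgical-complication endpoint is defined without reference to treatment-emergent status. SAP section 4 sends sparse data to listings, where the flagged event would be seen. Blank dates should also meet general cleaning: discrepant data are queried (protocol 7.1), source data are verified (7.3), and analysis follows a cleaned and locked database (SAP 2.4).

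Most of this stands, and it rules out several stronger readings.

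- A reader might infer that a blank date by itself removes an event. The AND condition prevents that.
- A reader might infer that removed events vanish from the report. They are listed with a flag.
- A reader might infer that the rule can only push incidence down. That holds from Study Day 1; before first dose, a pre-dose event with any other action entry is counted as treatment-emergent, which pushes the other way.
- A reader might infer from the diary conflict that dose dates will be lost. Protocol 4.5.5 has the diary record "type, and dose of each injection, if any, including emicizumab", and SAP 4.6.1 relies on it for dosing after discharge, while the diary footnote in protocol Appendix 1 (repeated in SAP Appendix 2) has it record "dose of bypassing agent, if any, excluding emicizumab". These passages must be reconciled, but that is a separate inconsistency. Both classifying entries sit on the adverse event page, and nothing says that the dose date there is taken from the diary.
- The fact that the sponsor does not supply emicizumab (protocol 4.3.3) makes incomplete dosing records conceivable. It does not show that they occur.

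What the defence leaves unanswered is that the rule applies in a period where, by the protocol's own requirement, it has no correct use. General data cleaning may reduce blank dates, but SAP 4.6.2 still says how to classify those that remain, and from Study Day 1 that classification is wrong.

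**Conclusion.** The point holds as a minor one. SAP 4.6.2 substitutes a pair of entries for a date comparison and does not limit the rule to the interval between consent and first dose. From Study Day 1 in operated patients, it can only wrongly remove on-drug events from the treatment-emergent tables. This assumes that the loading-dose requirement was met; a patient operated on without prior emicizumab would be a protocol deviation.

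The frequency cannot be computed from the documents, and no claim is made that incidence in this trial is in fact understated. The 5-point fall at n = 20 is arithmetic on one assumed misclassified patient with no other treatment-emergent event. The study is descriptive and tests no hypothesis, so no inference turns on this, only the accuracy of the safety tables.

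**What to change.** Replace the two-entry rule in SAP 4.6.2 with a date-based one:

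1. An event is treatment-emergent if its onset is on or after the first emicizumab dose.
2. In operated patients, every event from Study Day 1 is treatment-emergent.
3. If dose timing is unknown, count the event as treatment-emergent unless records show no dose before onset, and query the blank date before database lock.
4. Keep the non-treatment-emergent flag only for events between consent and a documented first dose.

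The cost is one derivation rule and the matching SAP wording, with no new visits or procedures. The documents do not show a dedicated first-dose field. However, protocol 4.4 already collects hemostatic medication from the week before emicizumab was started, so sites need to know when it began, and step 3 covers cases where the date is still lacking. Treatment-emergent counts may rise slightly, including an occasional pre-dose event whose timing cannot be established.
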